Name of the principal investigator at the sub-center:

Signature: Date: Year Month Day

Signature: Date: Year Month Day

Sponsor/Lead Organization

corporate name		Changzheng Hospital Affiliated to Naval Medical University	
project leader		[name]	
Contact address	[name]	zip code	200003
[contact]	cellphone	[name]
portraiture	[name]	E-mail	[contact]

Cooperative Unit

Company/Unit Name		Innovent Biologics (Suzhou) Co., Ltd.	
project leader			
Contact address		zip code	
telephone		cellphone	
portraiture		E-mail	

Company/Unit Name		Chia Tai Tianqing Pharmaceutical Group Co., Ltd.	
project leader			
Contact address		zip code	
telephone		cellphone	
portraiture		E-mail	

scenario summary	
scenario name	A phase II study of anlotinib plus sintilimab as first-line treatment for advanced non-liver metastatic colorectal cancer
Program number	APICAL-CRC2
version number	1.0
date	2025-12-8
Sponsor	Shanghai Changzheng Hospital
indication	Advanced colorectal cancer
Estimated study duration	The study is scheduled from December 2025 to December 2026. Enrollment for this research project is planned to commence in December 2025 and is expected to conclude in December 2026. Data analysis will be completed in June 2026, with the total trial duration approximately 1.5 years.
purpose of research	The efficacy of anlotinib combined with sintilimab as first-line therapy for advanced non-hepatic metastatic colorectal cancer was evaluated using the investigator-assessed objective response rate (ORR).
Total number of cases	The sample size calculation was based on the margin of confidence compared with historical controls, assuming an ORR of 70% in this study and an ORR rate of 50% in the historical controls. In the ITT analysis set, according to the Simon two-stage design, with a one-sided $\alpha=0.05$ and statistical power=0.8, the calculated sample size was 37 cases.
Case selection criteria	
Inclusion criteria:
 
 • Patients with advanced colorectal adenocarcinoma confirmed by histology or cytology; • Patients without liver metastases who have explicitly refused chemotherapy; • Patients who have not received systematic therapy or have developed metastasis or recurrence more than 12 months after the completion of adjuvant therapy; • The patient has at least one measurable lesion (per RECIST 1.1 criteria); • Patients who have undergone local radiotherapy at least 3 weeks prior to initial drug therapy are eligible for enrollment; however, RECIST-evaluated

	
lesions must not be within the radiotherapy field.
 
 • The patient must be at least 18 years of age; • Physical condition: ECOG score 0-1; • Life expectancy ≥ 12 weeks; • The patient must have the capacity to understand and voluntarily sign a written informed consent form; • Women of childbearing age must have a negative pregnancy test result within 7 days prior to initiating treatment. Both the patient and their spouse must use contraception during the study period. 
Exclusion criteria:
 
 • Patients who underwent major surgery or sustained severe trauma within 4 weeks prior to the initial medication administration; • Patients with hypersensitivity to any component of the study protocol; • Patients planning for pregnancy or already pregnant; • Patients with brain metastases who cannot accurately describe their condition; • Patients with autoimmune diseases or organ transplants; • Received immunosuppressive therapy within 2 weeks prior to treatment initiation (excluding inhaled corticosteroids or prednisone ≤ 10 mg/day, or other steroid hormones at physiologically equivalent doses); • Planning to receive a live attenuated vaccine within 4 weeks prior to study initiation or during the study period; • The patient has received anlotinib or anti-PD-1/PD-L1 monoclonal antibody therapy, or other treatments targeting T-cell co-stimulatory receptors or checkpoints; • Presence of the following conditions within 6 months prior to treatment initiation: myocardial infarction (MI), severe/unstable angina, NYHA class 2 or higher congestive heart failure, poorly controlled arrhythmias, etc.; • Abnormal laboratory findings: 
 -Absolute neutrophil count (ANC) $< 1,500/\text{mm}^3$; -Platelet count $< 75,000/\text{mm}^3$;
--	---

Total bilirubin>1.5 times the upper limit of normal
Alanine aminotransferase (ALT) and aspartate aminotransferase (AST)>2.5 times the upper limit of normal;
-Creatinine>1.5 times the upper limit of normal;

- Patients with other cancers (excluding advanced colorectal cancer) within five years prior to the initiation of treatment in this study. Exclusions include cervical carcinoma in situ, cured basal cell carcinoma, and bladder epithelial tumors.
- Patients with operable colorectal cancer (those who explicitly refuse surgery or are unsuitable for surgery may be enrolled);
- History of drug abuse, substance use, or alcohol dependence
- Lack of legal capacity or limited civil capacity;
- Other circumstances deemed unsuitable for enrollment by the investigator.

Exit criteria:

- Withdrawal requested by the patient or their legal representative;
- According to the investigator's opinion, the patient's continued participation in the study would be detrimental to their health;
- Patients with severe non-adherence or serious protocol violations;
- The patient is pregnant, and pregnancy should be reported as a serious adverse event;
- When other diseases occur during the study and the investigator determines that the condition will significantly affect the assessment of the patient's clinical status, necessitating discontinuation of the protocol;
- Presence of other malignant tumors requiring treatment;
- Patients who were lost to follow-up;
- Use of prohibited drugs or other medications that the investigator deems may cause toxic reactions or bias the study results;
- Patient death.

Note: Detailed records of the reasons and dates for withdrawal should be maintained for participants who withdraw during the study, and the withdrawal rate should be statistically analyzed upon study completion. Participants who withdraw from the study will receive appropriate treatment measures based on the judgment of the investigators at each center.

Research Phase and Steps	
1) December 2025 – January 2026: Obtain ethical review approval, screen and identify patients clinically diagnosed with advanced non-hepatic metastatic colorectal cancer;
 
2) February 2026 – June 2026: Informed consent was obtained from the selected population meeting inclusion/exclusion criteria, followed by treatment and evaluation.
 
3) July 2026 – December 2026: Complete enrollment of study cases; collect efficacy and safety data from patients who signed informed consent forms;
 
4) January 2027 – June 2027: Refine the data, correct errors, and perform statistical analysis.

statistical analysis	
sample size estimation
 
The sample size calculation was based on the margin of confidence compared with historical controls, assuming an ORR of 70% in this study and an ORR rate of 50% in the historical controls. In the ITT analysis set, according to the Simon two-stage design, with a one-sided $\alpha=0.05$ and statistical power=0.8, the calculated sample size was 37 cases.
 
Statistical analysis of research data
 
Statistical analysis was performed using SPSS software. Between-group and within-group comparisons were conducted using t-tests, with statistical significance defined as $p<0.05$.

Abbreviations Table

abbreviation	definition
AE	adverse event
ANC	Absolute neutrophil count
BID	twice daily
CBC	CBC
CI	confidence interval
CR	complete remission
CRR	complete remission rate
CT	computerized tomographic scanning
DOR	Duration of relief
ECG	electrocardiogram
ECOG	Eastern Cooperative Oncology Group
EFS	event-free survival
FDA	U.S. Food and Drug Administration
HBcAb	HBcAb
HBsAg	hepatitis B surface antigen
HBV	hepatitis B virus
HCV	HCV
IEC	independent ethics committee
IHC	immunohistochemical

IRB	institutional review board
FOLFIRI	5-FU, Iletixan, Lysine Folate
NCI-CTCAE v5.0	National Cancer Institute Common Terminology Criteria for Adverse Events, Version 5.0
NYHA	New York Heart Association
ORR	overall remission rate
OS	overall survival
PD	PD
PET	Positron Emission Tomography
PFS	progression-free survival
PR	partial remission
PT	Preferred term
QTc	Calibrated QT interval
SAE	Serious adverse events
SD	The disease is stable.
TEAE	Adverse events occurring during treatment
TRAЕ	adverse events related to treatment
ULN	ULN

catalogue

1. Introduction	3
2. Research Objective	5
3. Research Content	5
3.1 Research Design and Planning	5
3.2 Control	5
3.3 Selection of Study Population	5

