Based on the aforementioned findings, the combination of immune checkpoint inhibitors and anti-angiogenic TKIs is expected to generate potent synergistic antitumor effects. This strategy opens a new avenue for "chemotherapy-free" treatment of mCRC when the immune system is functional, particularly worthy of exploration in first-line therapy for mCRC. To preliminarily evaluate the efficacy and safety of anlotinib combined with sintilimab in first-line treatment of mCRC patients, we conducted the APICAL-CRC study [26], enrolling a total of 30 patients. The clinical objective response rate (ORR) was 48.3%, the disease control rate was 89.7%, with median progression-free survival (mPFS) and median overall survival (mOS) of 8.6 months and 22.9 months, respectively. Subgroup analysis revealed that the ORR in patients without liver metastases reached 70%, with mPFS of 14.9 months, whereas the ORR in patients with liver metastases was only 36.8%, significantly lower than that in patients without liver metastases. These results are consistent with previous studies (in the LEAP-017 study, the ORR for lenvatinib combined with pembrolizumab in patients with liver metastases was only 4.8% [14], while in the REGONIVO (USA) study, the ORR in patients with liver metastases was 0% [27]). Patients with better physical performance scores (ECOG PS 0 – 1) achieved an ORR of 66.7%, superior to those with ECOG PS 2 (21.4%). Patients carrying ARID1A mutations or those predicted to have a higher ORR (100% vs. wild-type 40%) also demonstrated better outcomes. In terms of safety, the incidence of treatment-related adverse events (TRAEs) of grade ≥ 3 with anlotinib plus sintilimab was only 13.3% (significantly lower than the 50%–70% observed with standard chemotherapy regimens). Adverse events such as hand-foot

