syndrome and hypertension were manageable, with no treatment-related deaths. This regimen provides a new option for chemotherapy-free treatment in patients with advanced colorectal cancer. Based on the preliminary results of the APICAL-CRC study, we plan to further screen the optimal patient population for subsequent research in advanced colorectal cancer patients. The enrolled patients will be limited to those without liver metastases and with a PS score of 0-1. Additionally, molecular biomarker analysis will be conducted, particularly stratified analysis based on ARID1A mutation status, to provide new strategies and methods for precision treatment of advanced colorectal cancer.

2. Research Objective

To evaluate the efficacy and safety of anlotinib combined with sintilimab as first-line treatment for non-hepatic metastatic advanced colorectal cancer.

Primary efficacy endpoint: ORR (objective response rate).

Secondary efficacy endpoints: safety, PFS (progression-free survival), OS (overall survival), and DPR (depth of tumor response).

3. Research Content

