3.2 Control

Eligible subjects will receive treatment according to the aforementioned protocol, with historical controls as the reference.

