3.7.1 Efficacy Indicators

Objective response rate (ORR) refers to the proportion of patients whose tumors shrink to a certain extent and sustain this reduction for a specified duration (primarily for solid tumors). It encompasses cases of complete response (CR) and partial response (PR).

Deepness of response (DpR): This refers to the percentage of maximum tumor shrinkage achieved during treatment compared to baseline. If a complete response (CR) is observed, the DpR is 100%.

Tumor response and disease progression will be assessed by investigators according to the RECIST criteria.

Progression-free survival (PFS) refers to the time from enrollment until tumor progression or death.

Overall survival (OS) refers to the time from randomization to death from any cause.

The duration of response maintenance was calculated for all patients who achieved confirmed RECIST-standardized PR or CR. The response maintenance period was defined as the time from the first recorded PR or CR until death or disease progression (whichever occurred first). For patients who were still alive and disease-free as of the analysis date, the cutoff date was set as the date of their last radiological assessment.

This study also explores the relationship between molecular markers and therapeutic efficacy and safety.

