5.1.3.1 Primary Efficacy Analysis

The primary endpoint was the objective response rate (ORR). The objective response rate refers to the proportion of patients who achieved tumor shrinkage of a certain size and maintained it for a specified duration, including cases with complete response (CR) or partial response (PR). The Kaplan-Meier method was used to derive the expected survival curves for patients in the treatment group.

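### The analysis methods the protocol names (t-tests with no variable or side, and Kaplan-Meier curves under the primary ORR analysis) do not match its one-sided Simon sizing of ORR 70% vs 50%

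*Protocol*

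**What the plan says.** **Sizing.** The synopsis (Total number of cases, repeated under statistical analysis) assumes an ORR of 70% against 50% in historical controls. It derives 37 cases "according to the Simon two-stage design, with a one-sided" alpha of 0.05 and power 0.8. Section 3.2 confirms that all patients receive the combination, "with historical controls as the reference".

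**Analysis of the data.** The next paragraph of the synopsis names SPSS and then: "Between-group and within-group comparisons were conducted using t-tests, with statistical significance defined as" p<0.05. No variable is named, and no side. No other hypothesis test is named anywhere in the protocol.

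**Primary analysis.** Section 5.1.3.1 defines ORR as the proportion with CR or PR and then gives one method: "The Kaplan-Meier method was used to derive the expected survival curves for patients in the treatment group".

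**Markers.** The Introduction plans molecular analysis, "particularly stratified analysis based on ARID1A mutation status". Section 3.7.1 adds: "This study also explores the relationship between molecular markers and therapeutic efficacy and safety".

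**Denominator.** The sizing refers to the ITT set. Section 5.1.1 defines that set as patients who received at least 2 cycles.

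**The concern.** ORR is a yes/no outcome, compared with a fixed historical rate in a single treated group. A between-group t-test has no second arm to act on. Kaplan-Meier curves describe time to an event and neither estimate nor test a response proportion. The rule that generated N = 37 therefore appears in the sizing but not in the analysis.

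This goes beyond detail left to a SAP. The protocol does state methods under its own analysis headings, and they are not the ones its design requires. A SAP that named an exact binomial rule would still leave both sentences in conflict with it.

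Two things are at stake. With no side attached to p<0.05, a result of 24 of 37 could be called a success or a failure. And because the t-test sentence has no limit, it could be taken to cover comparisons of response between a very small marker group and the rest.

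**Working it through.** **1. Reproduce the 37.** Inputs from the synopsis: p0 = 0.50, p1 = 0.70, one-sided alpha 0.05, power 0.80. A Simon design stops if X1 <= r1 of n1 and rejects if the total exceeds r of N. Its rejection probability is the sum over x > r1 of P(X1 = x) * P(X2 > r - x), evaluated at p0 for alpha and at p1 for power.
- Full enumeration finds no qualifying two-stage design for N from 20 to 36.
- At N = 37 there are 358 qualifying (n1, r1) pairs. All have r = 23, that is, success at 24 or more.
- The minimax choice with the lowest expected size is 12/23 then 23/37: alpha 0.0482, power 0.801.
- Normal approximation: ((1.645*0.5 + 0.842*0.458)/0.2)^2 = 36.5, so 37. With 1.96 for a two-sided test it is 46.6, so 47.

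The 37 is correct and fits only a one-sided test. The inputs fix the final bar and leave only the stage-1 boundary open.

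**2. What the missing side does to the primary test.** Exact binomial, n = 37, p0 = 0.5:

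| Responses | One-sided p | Two-sided p | Power at 70% if this is the bar (with the 12/23 stop) |
|---|---|---|---|
| 24 | 0.0494 | 0.0989 | 0.801 |
| 25 | 0.0235 | 0.0470 | 0.697 |

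A literal one-sample t-test on 0/1 responses uses t = (x/37 - 0.5)/sqrt((x/37)(1 - x/37)/36).
- 23/37: one-sided p = 0.071.
- 24/37: t = 1.87, one-sided p = 0.035, two-sided p = 0.070.
- 25/37: two-sided p = 0.031.

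The cut-offs are the same as for the exact test: 24 one-sided, 25 two-sided. The side decides the bar; the choice of t-test does not.

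**3. The t-test on response by marker, if it were applied there.** The Introduction reports the earlier trial as "enrolling a total of 30 patients. The clinical objective response rate (ORR) was 48.3"%. No count out of 30 gives that figure; 14/29 does. With the ARID1A figures ("those predicted to have a higher ORR (100% vs. wild-type 40%) also demonstrated better outcomes"), k + 0.4*(29 - k) = 14 gives k = 4, a split of 4/4 and 10/25. That is 4/29 = 13.8%, or about 5 of 37. Assumed range: 4 to 6 carriers of 37, with 8 to 10 as a sensitivity check. Chance of p<0.05 (two-sided) with no true difference and a common ORR of 65% or 70%, by full enumeration:

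| Carriers of 37 | Unequal-variance t | Pooled t | Fisher |
|---|---|---|---|
| 4 to 6 | 9.3% to 24.7% | 3.2% to 4.5% | 1.5% to 2.2% |
| 8 to 10 | 5.8% to 7.5% | 4.3% to 5.1% | 2.8% to 3.2% |

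Example with 26/37 responding overall, 5/5 vs 21/32. The 5/5 group has zero variance, so the unequal-variance t = 0.344/sqrt(0.656*0.344/31) = 4.03, p = 0.0003. Pooled t gives p = 0.12 and Fisher p = 0.29.

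**4. The denominator.** The bar of 24 belongs to n = 37. If the 2-cycle rule of 5.1.1 left 35 patients, the single-stage exact cut-off would be 23 (one-sided p = 0.045). Keeping 24 would give power 0.65 at 70%.

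**The case against.** - **The primary test is not harmed at the stated side.** One-sided 0.05 stands in the same synopsis cell, just before the t-test sentence, and at that level the bar and the power do not move. This stands. A reader might infer that the trial has only 70% power, but that needs the later sentence to replace the stated side silently, and nothing says that it does.
- **Part of this is SAP detail.** Naming a Simon design with p0, p1, alpha and side already implies a decision rule, and the Kaplan-Meier sentence is most likely misplaced. Both points are fair. What remains is that the methods actually written under the analysis headings are the wrong ones for a binary endpoint.
- **The marker comparison is an inference.** The t-test sentence does not mention markers. The Introduction and 3.7.1 describe stratified, exploratory work and promise no significance test. The between-group wording may be left over from a two-arm template, since 5.1.2 and 5.1.3.2 also speak of randomization. The inflation needs the unequal-variance form and very few carriers. The carrier count assumes that all 29 were genotyped and carries over to a different population. The ECOG rates in the same paragraph (66.7% and 21.4%) fit 10/15 and 3/14, which is 13/29 and not 14/29, so those subgroup figures are a weak base. All of this stands, and the 25% figure should not carry the point.
- **The stage-1 look raises accrual questions.** It does, but that is a separate matter of interim design.

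**Conclusion.** The stated methods do not match the design and should be corrected. The sample size is right, and at the sizing's own one-sided 0.05 the bar (24 of 37) and the power (about 0.80) are unaffected. The fall to 25 of 37 and power of about 0.70 is conditional on reading p<0.05 as two-sided.

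The marker figures are conditional on more: that a significance test is done, that it is an unequal-variance t-test, and that carriers number 4 to 6 (9% to 25%) or 8 to 10 (about 6% to 7.5%). A pooled t-test stays close to or below 5% throughout. The comparison is exploratory and cannot change the trial's main conclusion.

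A reader might also infer that PFS or OS will be analysed by t-test. No section says so. Nor is a t-test wrong everywhere: it can serve for a continuous measure such as depth of response.

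This is worth fixing before data are seen, because a success rule written down afterwards can look chosen to suit the result.

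**What to change.** 1. In 5.1.3.1, state the primary analysis as the exact Simon decision rule at one-sided 0.05 for H0: ORR <= 50%, with success at 24 or more of 37, and give the stage-1 boundary actually used. The 12/23 boundary is the minimax choice, for the sponsor to confirm.
2. Fix the denominator: all 37 enrolled and treated patients, with those not evaluable counted as non-responders, and reconcile the 2-cycle ITT definition in 5.1.1 with this. Otherwise, state that the cut-off will be recomputed for the actual n.
3. Move the Kaplan-Meier sentence to PFS, OS and duration of response.
4. In the synopsis, limit t-tests to named continuous variables such as depth of response. Use Fisher's exact test for any comparison of response proportions by marker status.
5. State the side of every p-value.

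The cost is a few sentences, with no change to N, alpha or power and no extra data. How accrual is handled while stage-1 responses are awaited should be settled separately.

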Colorectal cancer (CRC) is the third most common malignant tumor globally and the second leading cause of cancer-related mortality [1]. Despite recent advances in CRC research, approximately 15%-30% of patients present with metastatic lesions at initial diagnosis, and an additional 20%-50% of patients with locally advanced CRC will eventually develop metastatic disease [2]. The standard first-line treatment for metastatic colorectal cancer (mCRC) is fluorouracil-based chemotherapy combined with anti-EGFR/VEGF targeted agents, yet the prognosis remains poor, with a median overall survival of only about 2 years [3,4]. Moreover, some mCRC patients may be ineligible for standard doublet or triplet chemotherapy combined with targeted therapy due to factors such as advanced age, poor physical status, comorbidities, or personal preferences [5]. Exploring novel, highly effective, and low-toxicity treatment regimens holds significant clinical importance for these patients. In recent years, immune checkpoint inhibitors have emerged as a promising treatment option for mCRC, particularly for patients with DNA mismatch repair (dMMR) or high microsatellite instability (MSI-H) characteristics [6-8]. However, most pMMR/MSS mCRC patients exhibit primary resistance to immune checkpoint inhibitors due to the presence of immune deserts or immune rejection microenvironments [9]. To enhance the efficacy of immune checkpoint inhibitors in pMMR/MSS patients, a highly promising research direction is the combination of immunomodulatory antineoplastic agents with immunotherapy [10]. Anti-angiogenic drugs can directly or indirectly transform an immunosuppressive microenvironment into an immunostimulatory one, suggesting that the combination of immune checkpoint inhibitors with anti-angiogenic agents may produce synergistic antitumor effects [11,12]. For instance, the REGONIVO trial demonstrated that the combination of regorafenib and nivolumab exhibited controllable safety and encouraging antitumor activity in patients with refractory colorectal cancer [13]. However, in the LEAP-017 study, which compared lenvatinib plus pembrolizumab versus regorafenib or TAS-102 in previously treated, chemotherapy-resistant metastatic colorectal cancer patients, the primary endpoint was not met [14]. Patient characteristics (e.g., prior treatment history), treatment modalities (e.g., subsequent regimens), and performance of the control group may have influenced the results of the LEAP-017 trial. Although the clinical value of this regimen in subsequent treatments remains questionable, its potential to provide clinical benefits for immunocompetent first-line patients warrants further exploration.

Anlotinib is an oral tyrosine kinase inhibitor (TKI) that targets vascular endothelial growth factor receptors 1/2/3, epidermal growth factor receptors 1/2/3, FGFR, and c-Kit,

demonstrating broad-spectrum antitumor activity in various cancers [15-17]. Multiple clinical trials have shown therapeutic potential in patients with metastatic colorectal cancer (mCRC) [18,19]. A retrospective study evaluated the feasibility and tolerability of anlotinib combined with a PD-1 inhibitor in chemotherapy-resistant mCRC patients, revealing significant efficacy and favorable safety profile in this patient population [20]. Sintilimab, a fully humanized IgG4 monoclonal antibody, has demonstrated clinical benefits in non-small cell lung cancer (NSCLC) and hepatocellular carcinoma (HCC) by blocking the interaction between PD-1 and its ligand [21,22]. Previous studies have confirmed that the combination of sintilimab and anlotinib forms a novel chemotherapy-free regimen applicable to diseases such as cervical cancer and lung cancer [23,24]. Additionally, the combination of sintilimab and furquintinib has shown promising prospects in patients with refractory colorectal cancer, further suggesting its potential value when combined with anti-angiogenic TKIs [25].

Based on the aforementioned findings, the combination of immune checkpoint inhibitors and anti-angiogenic TKIs is expected to generate potent synergistic antitumor effects. This strategy opens a new avenue for "chemotherapy-free" treatment of mCRC when the immune system is functional, particularly worthy of exploration in first-line therapy for mCRC. To preliminarily evaluate the efficacy and safety of anlotinib combined with sintilimab in first-line treatment of mCRC patients, we conducted the APICAL-CRC study [26], enrolling a total of 30 patients. The clinical objective response rate (ORR) was 48.3%, the disease control rate was 89.7%, with median progression-free survival (mPFS) and median overall survival (mOS) of 8.6 months and 22.9 months, respectively. Subgroup analysis revealed that the ORR in patients without liver metastases reached 70%, with mPFS of 14.9 months, whereas the ORR in patients with liver metastases was only 36.8%, significantly lower than that in patients without liver metastases. These results are consistent with previous studies (in the LEAP-017 study, the ORR for lenvatinib combined with pembrolizumab in patients with liver metastases was only 4.8% [14], while in the REGONIVO (USA) study, the ORR in patients with liver metastases was 0% [27]). Patients with better physical performance scores (ECOG PS 0 – 1) achieved an ORR of 66.7%, superior to those with ECOG PS 2 (21.4%). Patients carrying ARID1A mutations or those predicted to have a higher ORR (100% vs. wild-type 40%) also demonstrated better outcomes. In terms of safety, the incidence of treatment-related adverse events (TRAEs) of grade ≥ 3 with anlotinib plus sintilimab was only 13.3% (significantly lower than the 50%–70% observed with standard chemotherapy regimens). Adverse events such as hand-foot

syndrome and hypertension were manageable, with no treatment-related deaths. This regimen provides a new option for chemotherapy-free treatment in patients with advanced colorectal cancer. Based on the preliminary results of the APICAL-CRC study, we plan to further screen the optimal patient population for subsequent research in advanced colorectal cancer patients. The enrolled patients will be limited to those without liver metastases and with a PS score of 0-1. Additionally, molecular biomarker analysis will be conducted, particularly stratified analysis based on ARID1A mutation status, to provide new strategies and methods for precision treatment of advanced colorectal cancer.

2. Research Objective

To evaluate the efficacy and safety of anlotinib combined with sintilimab as first-line treatment for non-hepatic metastatic advanced colorectal cancer.

Primary efficacy endpoint: ORR (objective response rate).

Secondary efficacy endpoints: safety, PFS (progression-free survival), OS (overall survival), and DPR (depth of tumor response).

3. Research Content

